11.1 Primary Objective(s)

Primary Objective #1

Evaluate the impact of the intervention on the diagnosis of SND.

Endpoint Definition

The absolute change in the proportion of subjects diagnosed with SND at pre-specified time points ($\% = \text{number diagnosed}/\text{number enrolled} \times 100$ at time point t where $t = 6, 12$, and any additional 6-month interval for which there is sufficient follow-up information) and the absolute change in the number of subjects diagnosed with SND per person-year.

Analysis Methods

A. Statistical Methodology

To compare the proportion of subjects with an SND diagnosis pre-intervention (Phase I) to the proportion post-intervention (Phase II), a chi-square test will determine statistical significance. The proportion of subjects diagnosed will be evaluated at multiple time points because the time to diagnosis is expected to vary by geography. Thus, times are pre-specified starting at 6 months and any additional 6-month interval thereafter for which there is sufficient follow-up data available to compare study phases. Proportions calculated at all available time points will be reported. Additionally a Poisson regression will compare the average number of subjects with an SND diagnosis in Phase I and Phase II where the subject time in study is treated as an offset in the model. The above described tests will be performed separately within geography/country as well as overall.

B. Determination of Patients/Data for Analysis

All subjects that are enrolled in the study will be included in the determination of the proportion estimates. The proportion estimates will be calculated based on information from fixed time points at 6 months of follow-up, 12 months of follow-up, and any additional 6-month interval thereafter for which there is sufficient follow-up data available to compare study phases. The number of subjects that obtain a SND diagnosis by pre-specified time point $t= 6, 12, \text{ etc.}$, is included in the numerator and the number of subjects enrolled is included in the denominator.

Sample Size Methods and Assumptions

The proportion of SND diagnoses in bradycardia subjects is currently unknown within the study geographies. The PANARM HF study of 2000 subjects found that 146 out of 331 bradycardia subjects (44%) had SND and that 15 (10%) of SND subjects opted for IPG therapy. The power calculations conservatively assume that the SND diagnosis will be 20% at six months of follow-up, or equivalently an SND incidence of 0.4 diagnoses per person-year. Thus, the margin of error will be $\pm 4\%$ in a sample of 500 subjects per geography/country, based on a 95% confidence interval. If 500 subjects are collected in Phase I and 1000 subjects are collected in Phase II, assuming a type I error of 0.05 and power of 0.90, a chi-square test will detect an increase in SND diagnosis of at least 8%. For example, the study will find a statistically significant difference between a Phase I SND percentage of 20% at 6 months and a Phase II SND percentage of 28% at 6 months. The Poisson regression for the same scenario has a power of 0.95 to compare SND incidence of 0.4 versus 0.56 diagnoses per person-year. If the proportion of SND diagnoses is smaller than 20%, there will be more power to detect significant differences in the diagnosis proportion. Thus, the Phase II sample size will be recalculated within geography/country once Phase I data collection is complete. It is expected that the study attrition rate may be 10-15% of the study population. To account for attrition, *the sample size for Phase I will be 550 subjects per geography/country and for Phase II may be 1100 subjects per geography/country.*

Primary Objective #2

Evaluate the impact of the intervention on SND subjects receiving an indicated IPG device.

Endpoint Definition

The absolute change in the proportion of subjects receiving indicated therapy at pre-specified time points (% = number receiving IPG/number with SND diagnosis $\times 100$ at time point t where $t= 3, 6, \text{ and any additional 3-month interval for which there is sufficient follow-up information}$) and the absolute change in the number of subjects implanted per person-year.

Analysis Methods

A. Statistical Methodology

To compare the proportion of subjects that receive indicated therapy pre-intervention (Phase I) to the proportion post-intervention (Phase II), a Fisher's Exact test will determine statistical significance. A Fisher's exact test is recommended for smaller sample sizes. The proportion of subjects diagnosed will be evaluated at multiple time points because the time from diagnosis to implant is expected to vary by geography. Shorter time intervals will be used to evaluate the proportion of implants than for the proportion of diagnosis because implants typically occur more quickly than the SND diagnosis. Thus, times are pre-specified starting at 3 months and any additional 3-month interval thereafter for which there is sufficient follow-up data available to compare study phases. Proportions calculated at all available time points will be reported. Additionally, a Poisson regression will compare the average number of subjects with an implant where the subject time in study beginning at the time of SND diagnosis is treated as an offset in the model. The above described tests will be performed separately within geography/country as well as overall. Further, similar tests will compare the differences in the types of therapy received in Phase I and Phase II. For example, a Fisher's exact test will compare the frequency of dual chamber device use pre- and post-intervention.

B. Determination of Patients/Data for Analysis

The number of subjects that meet inclusion criteria and obtain an SND diagnosis shall be included in this analysis. The proportion estimates will be calculated based on information from fixed time points at 3 months of follow-up, 6 months of follow-up, and any additional 3-month interval thereafter for which there is sufficient follow-up data available to compare study phases. The number of subjects that obtain an IPG by pre-specified time point $t = 3, 6, \text{ etc.}$, will be included in the numerator and the number of subjects with an SND diagnosis will be included in the denominator.

Sample Size Methods and Assumptions

The proportion of IPG therapy in SND subjects is currently unknown within the study geographies. The PANARM HF study of 2000 subjects found that 146 out of 331 bradycardia subjects (44%) had SND and that 15 (10%) of SND subjects opted for IPG therapy. PANARM HF included symptomatic HF which is different than the IMPROVE Brady population. Thus, the percentages expected in IMPROVE Brady may differ from those observed in PANARM HF. Assuming that 20% of subjects will be diagnosed with SND, this suggests that there will be 100 SND subjects in Phase I and 200 in Phase II per geography/country. Further assuming that IPG therapy will be adopted by 10% of SND subjects at three months after diagnosis, or equivalently an IPG incidence of 0.25 diagnoses per person-year, this means that the margin of error will be $\pm 8.0\%$ in a sample of 100 subjects per geography/country, based on a 95% confidence interval. If there are 100 SND subjects in Phase I and 200 SND subjects in Phase II, assuming a type I error of 0.05 and power of 0.90, a Fisher's Exact test will detect an increase in IPG therapy of at least 16% at three months after diagnosis. This means that the objective will obtain statistical significance if 52 of 200 SND subjects in Phase II

opt for IPG therapy. The Poisson regression for the same scenario has a power of 0.95 to compare IPG incidence of 0.25 versus 0.625 implants per person-year. The power of this objective will improve if the percentage of SND diagnoses is larger than 20%. In order to better account for the proportion of SND diagnosis and IPG adoption per geography/country, the Phase II sample size will be recalculated within the geography/country once Phase I data collection is complete.

Stopping Guidelines for Futility

If Phase I of the study suggests that only 5% of enrolled subjects meet an SND indication and that only 5% of those indicated opt for IPG therapy, the study may close for futility at the end of Phase I within that geography/country. Suppose that the percent of SND diagnosis is 5% and that 5% of those indicated will opt for therapy. Assuming 500 subjects in Phase I, 5,440 subjects will be needed in Phase II to see an increase in the implant rate from 5% to 30%. This suggests a scenario with insufficient power to continue into Phase II.

11.2 Secondary Objectives

Secondary Objective #1

Describe the diagnosis and treatment of phase I subjects.

Endpoint Definition

The proportion of subjects receiving an SND diagnosis and the number of diagnosis that result in indicated therapy at pre-specified time points and the number of subjects diagnosed and implanted per person-year

Analysis Methods

A. Statistical Methodology

An exact 95% confidence interval of a binomial proportion at each pre-determined time point will be used to calculate the margin of error for the SND and IPG proportions in Phase I of the study.

B. Determination of Patients/Data for Analysis

All subjects that are enrolled in the study will be included in the determination of the proportion estimates of SND. The proportion estimates will be calculated based on information from fixed time points at 6 months of follow-up, 12 months, and any additional 6-month interval thereafter for which there is follow-up data available. The number of subjects that obtain a SND diagnosis by pre-specified time point $t= 6, 12, \text{ etc.}$, is included in the numerator and the number of subjects enrolled is included in the denominator. The number of subjects that meet inclusion criteria and obtain a SND diagnosis shall be included in the determination of the proportion estimates of IPG therapy. The proportion estimates will be calculated based on information from fixed time points at 3 months of follow-up, 6 months, and any additional 3-month interval thereafter for which there is follow-up

data available. The number of subjects that obtain an IPG by pre-specified time point $t= 3, 6$, etc., will be included in the numerator and the number of subjects with an SND diagnosis will be included in the denominator.

Secondary Objective #2

Evaluate the change in the time to diagnosis of SND before and after intervention.

Endpoint Definition

Time to diagnosis in days (date of diagnosis – date of enrollment); number of visits to diagnosis

Secondary Objective #3

Evaluate the change in the time to receiving an indicated IPG device for SND subjects before and after intervention.

Endpoint Definition

Time to treatment in days (date of implant – date of diagnosis); number of visits to treatment

Analysis Methods**A. Statistical Methodology**

For Secondary Objectives 2 and 3 above, the following statistical analysis is proposed. A stratified log-rank test of two Kaplan-Meier curves will determine if there is a significant difference in the time to endpoint before and after intervention. The stratification will occur by geography/country and also by site. Stratified Cox models may also be fit to examine independent variables of interest that may affect SND diagnosis, such as gender and age. Descriptive statistics will be used to characterize the number of visits that occur before an SND diagnosis and between the diagnosis and implant and further will examine number of visits separated by Phase, geography/country, type of enrolling physician, and possibly other baseline characteristics.

B. Determination of Patients/Data for Analysis

The subjects to include in the analysis of secondary objectives 2 and 3 are the same as specified for primary objectives 1 and 2 respectively.

Secondary Objective #4

Evaluate the Caregiver burden between pre-implant and 6 months post-implant

Endpoint Definition

Compare the difference in caregiver burden from pre-implant to 6 months post-implant

Analysis Methods**A. Statistical Methodology**

Descriptive statistics will be used to summarize the difference in caregiver burden between pre-implant and 6 months post-implant.

B. Determination of Patients/Data for Analysis

Subjects in Phase II who opt to receive an indicated therapy and are implanted with a market released pacemaker from the Medtronic family of devices will be followed from implant to 6 months post-implant. The primary caregiver of these subjects will be asked to complete a questionnaire that assesses caregiver burden at the time of implant and 6 months post-implant.

Secondary Objective #5

Evaluate change in Quality of Life (QOL) and functional status between pre-implant and 6 months post-implant.

Endpoint Definition

Compare the difference in QOL and functional status between pre-implant and 6 months post-implant.

Analysis Methods**A. Statistical Methodology**

Descriptive statistics will be used to summarize the difference in QOL and functional status between pre-implant and 6 months post-implant.

B. Determination of Patients/Data for Analysis

Subjects in Phase II who opt to receive an indicated therapy and are implanted with a market released pacemaker from the Medtronic Family of devices will be followed from implant to 6 months post-implant. These subjects will be asked to complete a questionnaire that assesses their QOL at the time of implant and 6 months post-implant.

[REDACTED]

[REDACTED]

[REDACTED]

[REDACTED]

[REDACTED]

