4.3 Study Design

There are two phases to IMPROVE Brady:

Phase I: This phase of the study serves as a control period. During Phase I physicians will assess and treat subjects per their site's standard care practice. Enrollment for Phase I is anticipated to occur for approximately 12 months but will continue until 550 subjects have been enrolled for the geography/country. For subjects enrolled during Phase I, collection of diagnostic assessment and implant data will be complete 6 months after the last enrollment for the geography/country. At that time, all Phase I subjects will be exited.

If a center becomes active after the geography/country enrollment goal for Phase I has been met or the center did not enroll at least 10 subjects before Phase I enrollment stopped then the center will enroll Phase I subjects until 10 subjects have been enrolled at that center. Once 10 subjects have been enrolled at the center, enrollment will stop and the subjects will be followed for a maximum of 6 months and exited from the study.

Phase II:

The objective of the IMPROVE Brady study is to provide investigators with comprehensive resources that may be adapted by the Principal Investigator and his/her colleagues to create a practice specific process improvement intervention to improve the quality of care for patients.

At the completion of Phase I, the Principal Investigator and co-investigators will complete an educational workshop and be given access to the IMPROVE Brady toolkit. In addition, the Principal Investigator and his/her colleagues are encouraged to adapt tools from the IMPROVE Brady toolkit to create a practice specific process improvement intervention.

Immediately following completion of the educational workshop, study investigators will receive written authorization from Medtronic that they are authorized to enroll subjects in Phase II. Enrollment during this phase is anticipated to occur for approximately 18 months per geography/country.

[figure not shown]
The IMPROVE Brady process improvement intervention toolkit may include an education workshop, diagnostic algorithm(s), patient video and tools for investigators to educate their patients on their disease state, available therapy options, and benefits and risks associated with the therapy options.

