During Phase II a patient survey assessing the subject's quality of life and functional status, will be completed by subjects meeting an SND indication for pacing therapy and being implanted with a market released pacemaker from the Medtronic family of devices. The patient survey must be completed before the implant procedure and again at 6 months post-implant.

The caregiver of the subject being implanted with the market released pacemaker from the Medtronic family of devices will be asked to participate in a caregiver survey. The purpose of the survey is to assess how providing care to the person receiving the pacemaker impacts the caregiver. Prior to completing the survey an Informed Consent or Patient Data Release will need to be signed by the caregiver. The caregiver survey will be completed prior to the implant procedure and again at 6 months post-implant. The same caregiver must complete the pre and post implant surveys of the same patient.

For subjects enrolled during Phase II collection of diagnostic assessment data will be complete 6 months after last enrollment for the geography/country. At that time, any subjects without a diagnosis will be exited from the study. Collection of implant data will be complete 6 months after the last Phase II diagnosis for the respective geography/country. Any subjects not implanted by the end of the 6 months will be exited from the study. The Geography/country study timeline (Figure 2) depicts the geography/country timeline.

Figure 2: Geography/country study timeline

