8.5.4.1. Analysis Methods

A. Statistical Methodology

A log-rank test of two Kaplan-Meier curves will determine if there is a significant difference in the time to diagnosis before and after intervention, within the South Asia geography. [REDACTED]

[REDACTED]

[REDACTED]

[REDACTED]

Cox models may also be fit to examine independent variables of interest that may affect SND diagnosis, such as gender and age. Descriptive statistics will be used to characterize the number of visits that occur before an SND diagnosis and further will examine number of visits separated by Phase, type of enrolling physician, and possibly other baseline characteristics. [REDACTED]

This document is electronically controlled. Printed copies are considered uncontrolled.

Confidential

B. Determination of Patients/Data for Analysis

The subjects to include in the analysis of Secondary Objective 2 in Section **Error! Reference source not found.** are the same as specified in Section **Error! Reference source not found.** for Primary Objective 1.

C. Additional Analyses

In addition to the time to event analysis, various additional analyses of the subjects will be explored, including a description of diagnostic tests performed when there is a delay in a patient's diagnosis. The endpoint is time to diagnosis and variables of interest are the different types of diagnostic tests. A table will be created with a format as follows:

Tests performed	SND dx 0-6 months	SND dx 6-12 months	SND dx 12-18 months
ECG	Number of tests, number of subjects		
Tilt table			
ILR			
Holter			
Average number of tests performed			

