8.5.5.1. Analysis Methods

A. Statistical Methodology

A log-rank test of two Kaplan-Meier curves will determine if there is a significant difference in the time to implant before and after intervention, within the South Asia geography. Descriptive statistics will be used to characterize the number of visits that occur between the diagnosis and implant and further will examine number of visits separated by Phase, type of enrolling physician, and possibly other baseline characteristics.

B. Determination of Patients/Data for Analysis

The subjects to include in the analysis of Objective 3 in Section **Error! Reference source not found.** are the same as specified in section **Error! Reference source not found.** for Primary Objective 2.

C. Additional Analyses

In addition to the time to event analysis, a Cox model will test covariates of interest that may include gender, age, HF, NYHA class and ejection fraction and the impact on time to implant. A characterization will also be provided that describes covariates of interest and whether or not the implant was CRT instead of an IPG

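### Visit counts are compared by phase with no common observation window: visits to implant tend to look higher in Phase II with unchanged practice, visits to diagnosis only if Phase II enrolls for longer

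*Protocol*

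**What the plan says.** Protocol 11.2 defines the endpoint of Secondary Objective 2 as "Time to diagnosis in days (date of diagnosis – date of enrollment); number of visits to diagnosis". For Secondary Objective 3 the second component is "number of visits to treatment". The times are analysed by Kaplan-Meier and log-rank. The visit counts are summarised only descriptively ("Descriptive statistics will be used to characterize the number of visits that occur before an SND diagnosis and between the diagnosis and implant"), and the Protocol "further will examine number of visits separated by Phase, geography/country, type of enrolling physician". The SAP does the same: section 8.5.4.1 for diagnosis ("further will examine number of visits separated by Phase, type of enrolling physician, and possibly other baseline characteristics") and section 8.5.5.1 for implant ("Descriptive statistics will be used to characterize the number of visits that occur between the diagnosis and implant"), also by phase. Section 6 of the SAP limits phase comparisons to South Asia.

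The closing rules are in Protocol 4.3. For Phase I, "collection of diagnostic assessment and implant data will be complete 6 months after the last enrollment for the geography/country". Centers that start late or have enrolled few subjects follow their Phase I subjects for at most 6 months. For Phase II, diagnosis data also close 6 months after last enrollment, but implant data stay open: "Collection of implant data will be complete 6 months after the last Phase II diagnosis for the respective geography/country".

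**The concern.** A count of visits up to an event is complete only for subjects who reached the event while data were being collected. If one phase stops collecting sooner, its slow cases, which tend to have the most visits, drop out of its summary and the mean falls. The phases then differ with no change in practice.

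Both objectives ask about change from before to after the intervention, so the by-phase summary is what a reader will use. For visits between diagnosis and implant, the distortion works against showing fewer visits after the intervention and could mask a real reduction. The plan handles unequal follow-up elsewhere: censoring in the Kaplan-Meier analysis, fixed time points for the primary proportions, and a time offset in the Poisson models. The visible text gives the visit counts nothing comparable. With one geography left, no second one can expose the artefact.

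**Working it through.** **1. The plan's own timing.** Phase I: 12 months of enrollment + 6 = 18 months = 1.5 years. Phase II: 18 (enrollment) + 6 (diagnosis) + 6 (implant) + 6 (post-implant visit) = 36 months = 3 years. The total is 4.5 years. These match the follow-up in Protocol section 4 and the duration in section 1.2, so the closing rules are read as intended.

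**2. Window per subject, diagnosis.** With uniform enrollment, Phase I subjects have 6 to 18 months and Phase II subjects 6 to 24. The chance that a diagnosis at month t (beyond 6) is captured is (18 − t)/12 in Phase I and (24 − t)/18 in Phase II. At t = 12 this is 6/12 = 0.50 against 12/18 = 0.67. At t = 18 it is 0 against 6/18 = 0.33. The closing rule is the same, so the difference comes only from enrollment length.

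**3. Window per subject, implant.** In Phase I the time left is closure minus diagnosis date, which can be close to zero. In Phase II it is never below 6 months. At the planned rates about 21% of Phase I diagnoses have under 3 months left for an implant, against none in Phase II. This difference is in the rule itself.

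**4. Simulation with unchanged practice.** Inputs from the Protocol and SAP: 20% diagnosed by 6 months and 10% of SND subjects implanted by 3 months. The constant monthly rates are −ln(0.80)/6 = 0.0372 and −ln(0.90)/3 = 0.0351. Assumptions: uniform enrollment, and one visit every 2 months, so visits = time/2 rounded up. The size was 3 million subjects per phase. In the shorter-delay rows only some subjects ever have the event, with the stated mean delays, calibrated to the same 20% and 10%.

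| Event speed | Enrollment I/II (months) | Visits to diagnosis, II v I | Visits diagnosis to implant, II v I |
|---|---|---|---|
| Constant rates | 12/18 | 3.45 → 4.17 (+21%) | 2.71 → 4.24 (about +57%) |
| Mean delays 6 and 3 months | 12/18 | +9% | +14% |
| Mean delays 2 and 1 months | 12/18 | about +1% | about +1% |
| Constant rates | 10/20 (SAP section 5) | +37% | +77% |
| Constant rates | 12/12 | none | about +37% |
| Constant rates | 12/10.4 | ratio 0.94 | not needed for sign |
| Constant rates | 12/6.2 | ratio 0.79 | +19% |

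The last two rows use SAP Table 3 entries of 570 and 343 subjects at the SAP's 55 per month: 570/55 = 10.4 and 343/55 = 6.2 months. They show what the sample size adaptation could produce if those rows alone set the Phase II size.

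**5. Second scale.** If visits accrue in proportion to time, and the printed rates of 0.4 and 0.25 per person-year are used, mean time to diagnosis among the diagnosed is 5.9 v 7.4 months (+25%). Mean time from diagnosis to implant among the implanted is 4.5 v 7.9 months (+75%). The printed 0.25 does not match 10% at 3 months (0.10/0.25 = 0.40); with 0.40 the implant excess is +72%, so the discrepancy hardly matters here.

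**6. After the fix.** Counting only diagnoses within 6 months of enrollment, and implants within 3 months of diagnosis in subjects with 3 months left, the Phase II/Phase I ratio is 1.00 for both counts in every scenario tried.

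**The case against.** **Direction for diagnosis.** A reader might infer that Phase II must show more visits on both endpoints. The documents do not support that for diagnosis. Phase I enrollment runs until its target is met, Phase II is to be resized from Phase I results, and South Asia's realised enrollment lengths are not given. The bias could be upward, absent or downward. This objection stands. It does not rescue the implant count, which was inflated at every enrollment length tried with constant rates.

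**Size.** Visit spacing is assumed, since Protocol 5.4 does not fix it. If visits cluster early (taking visits as 1 + log2(1 + months)), the constant-rate 12/18 excess falls to 6.5% for diagnosis and 20% for implant, and with mean delays of 6 and 3 months to 3% and 6%. A constant implant rate is also generous: Protocol 5.7 allows exit of SND subjects who will not be paced, and 11.1 expects implants to come faster than diagnoses. This stands, so only a range can be given.

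**The text.** The plan does not say in words that counts are limited to subjects with the event; Section B of each analysis names all enrolled and all SND subjects. That follows from what the count means, but nothing visible says how other subjects contribute. In SAP 8.5.4.1 a redaction follows the visit sentence, so handling of diagnosis visits may be specified there. No redaction appears in SAP 8.5.5.1.

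**Slow cases.** The SAP 8.5.4.1 table with 6-12 and 12-18 month columns might be read as proof that the sponsor expects many late diagnoses. It is an empty shell and shows only that they are possible.

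**Consequence.** The counts are descriptive and the tests of both objectives use log-rank, which allows for unequal censoring. This stands. Nor has it been shown how often a true reduction would be masked, because only the no-effect case was simulated.

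**Conclusion.** The point holds in a conditional form. For visits between diagnosis and implant, the phase comparison is biased by design: the closing rules differ and Phase II will tend to show more visits with unchanged practice. With 12/18-month enrollment and a visit every 2 months, the excess runs from about 57% (constant planned rates) through 14% (mean delay 3 months) to about 1% (mean delay 1 month). For visits to diagnosis, bias arises only if enrollment lengths differ: about 21% at 12/18 months with constant rates, none if equal, reversed if Phase II is shorter.

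The primary objectives and the log-rank results of Secondary Objectives 2 and 3 are not touched. What is at risk is the descriptive before-and-after reading of two stated endpoints.

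**What to change.** In SAP 8.5.4.1 and 8.5.5.1, add a sentence to each limiting the phase comparison of visit counts to a window both phases can complete:

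- **Diagnosis:** visits among subjects diagnosed within 6 months of enrollment.
- **Implant:** visits among subjects implanted within 3 months of diagnosis, restricted to those diagnosed at least 3 months before their phase or center closed.
- **Beside each count:** the number of subjects with and without the event in that window, by phase.
- **Later events:** listed, with no phase comparison.

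If a late-starting center closes before a subject has had 6 months, that subject cannot complete the diagnosis window and should be left out and counted.

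The cost is two sentences and a program filter. No new data are needed, and the 6- and 3-month points are already used for the primary objectives. The downside is that late events leave the comparison. The windowed count also still conditions on having the event, which the intervention aims to change, so it should be read beside the Kaplan-Meier result. A mean cumulative visit count adjusted for censoring would keep all subjects and is an acceptable alternative.
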